8.3.1 Time period and frequency for collecting AE and SAE information

All AEs, including adverse events of new onset, as well as worsening of baseline signs and symptoms will be collected throughout study period, from the signing of the informed consent form (ICF) until **30 days** following cessation of study treatment.

All SAEs and AESIs will be collected throughout the study period, from the signing of the informed consent form (ICF) until **90 days** following last administration of study treatment.

All SAEs and AESI will be recorded and reported to the Sponsor or designee immediately and under no circumstance should this exceed 24 hours, as indicated in Appendix 3 ([Section 10.3](#)). The Investigator will submit any updated SAE data to the Sponsor within 24 hours of it being available.

Investigators are not obligated to actively seek information on AEs or SAEs after conclusion of the study participation. However, if the Investigator learns of any SAE, including a death, at any time after a participant has been discharged from the study, and he/she considers the event to be reasonably related to the study intervention or study participation, the Investigator must promptly notify the Sponsor.

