9.4.1 General considerations

This study is not intended to explicitly test a hypothesis, 90% CIs will be provided for primary and secondary efficacy endpoints for descriptive purposes only.

All efficacy analyses will be performed on the efficacy population and analyzed by cohort and pooled cohorts (if applicable). Objective response rate, as well as all other efficacy variables will be derived using the local radiologist's/Investigator's assessment for all cohorts. Unless otherwise specified, the assessments are based on RECIST 1.1.

All safety analyses will be performed on the exposed population by cohort and overall (if applicable). A baseline value will be defined as the latest value or measurement taken up to the first administration of the IMP.

The analysis period will be divided into 3 segments:

- The pre-treatment period is defined as the time from when the participants give informed consent to the first administration of the IMP.
- The on-treatment period (ie, treatment-emergent period) is defined as the time from the first administration of IMP up to 30 days after the last administration of IMP.
- The post-treatment period is defined as the time from the 31 days after the last administration of IMP.

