9.4.3.5 Adverse events

All AEs will be categorized according to NCI-CTCAE v5.0 (except for CRS and ICANS that will be graded using ASTCT criteria) and classified by system organ class (SOC) and Preferred Term (PT) according to the latest available version of the Medical Dictionary for Regulatory Activities (MedDRA).

- Pre-treatment AEs are defined as any AEs occurring during the pre-treatment period.
- Treatment-emergent AEs are defined as AEs that develop, worsen (according to the Investigator's opinion), or become serious during the treatment-emergent period.
- Post-treatment AEs are defined as AEs that are reported during the post-treatment period.

For participants with multiple occurrences of the same PT, the maximum grade will be used.

The primary focus of AE reporting will be on TEAEs. Pre-treatment and post-treatment AEs will be described separately.

Treatment-emergent adverse events:

An overall summary of TEAEs will be provided. The number and percentage of participants experiencing any of the following will be provided:

- TEAEs
- Grade ≥ 3 TEAEs
- Grade 5 TEAEs (any TEAE with a fatal outcome during the treatment-emergent period)
- Serious TEAEs
- Serious treatment-related TEAEs
- TEAEs leading to permanent partial intervention discontinuation (any of the IMP components)
- TEAEs leading to permanent full intervention discontinuation
- Treatment-related TEAEs
- Treatment-related TEAEs Grade ≥ 3

Number and percentage of participants experiencing TEAEs by primary SOC and PT will be summarized by NCI-CTCAE v 5.0 or ASTCT grade (all grades and Grade ≥ 3). Missing grades, if any, will be included in the "all grades" category. Similar summaries will be prepared for treatment-related TEAEs, TEAEs leading to permanent discontinuation of SAR444245, or permanent discontinuation of other anticancer therapies in combination, TEAEs leading to full intervention discontinuation, TEAEs leading to dose modification, serious TEAEs, TEAEs with fatal outcome, AESIs, and AEs/SAEs occurring during the post-treatment period. In addition, the number (%) of participants with any Grade 5 AE (TEAE and post-treatment) will be summarized.

The following deaths summaries will be generated:

- Number and percentage of participants who died by study period (treatment-emergent period, post-treatment period) and reasons for death (disease progression, AE, or other reason).
- All TEAEs leading to death by primary SOC and PT showing number and percentage (%) of participants.

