6.5.4.4 Immune-related adverse events

AEs associated with pembrolizumab exposure may represent an immunologic etiology. These immune-related AEs (irAEs) may occur shortly after the first dose or several months after the last dose of pembrolizumab treatment and may affect more than one body system simultaneously. IrAEs are thought to be caused by unrestrained cellular immune responses directed at the normal host tissues. Therefore, early recognition and initiation of treatment is critical to reduce complications. Based on existing pembrolizumab clinical study data, most irAEs were reversible and could be managed with interruptions of pembrolizumab, administration of corticosteroids and/or other supportive care.

Investigators must be extremely vigilant and be ready to intervene early in the management of irAEs because the onset of symptoms of irAEs (eg, pneumonitis) may be subtle. For suspected irAEs, adequate evaluation should be performed to confirm etiology or exclude neoplastic, infectious, metabolic, toxin, or other etiologic causes. Additional procedures or tests such as bronchoscopy, endoscopy, skin biopsy may be included as part of the evaluation. Based on the severity of irAEs, withhold or permanently discontinue pembrolizumab and/or SAR444245 and administer corticosteroids.

SAR444245 may increase the incidence and severity of these events.

Dose modification and toxicity management guidelines for irAEs are provided in [Table 6](#). Of note, when study interventions are administered in combination, if the AE is considered immune-related, both drugs in the combination should be held according to recommended dose modifications. If a participant experiences several irAEs, the most conservative recommendation should be followed.

The CTCAE V5.0 must be used to grade the severity of AEs.

When pembrolizumab can be restarted, it should be administered at the initial planned dose and schedule as no modification is allowed:

- If the toxicity does not resolve or the criteria for resuming treatment are not met, the participant must be discontinued from all study drugs.
- If the toxicities do resolve and conditions are aligned with what is defined in [Table 6](#), the combination of SAR444245 or pembrolizumab may be restarted at the discretion of the investigator. In these cases where the toxicity is attributed to the combination or to SAR444245 alone, re-initiation of pembrolizumab as a monotherapy may be considered after communication with the Sponsor.

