8.3 ADVERSE EVENTS (AES), SERIOUS ADVERSE EVENTS (SAES) AND OTHER SAFETY REPORTING

Please refer to the master protocol.

8.3.1 Time period and frequency for collecting AE and SAE information.

Please refer to the master protocol for AEs and serious adverse events (SAEs) collection. For participants in Cohort A irAEs will be collected until 90 days following last administration of study treatment regardless of whether or not another anticancer therapy is initiated.

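### SAEs and AESIs are collected to day 90 after last dose, but the overall safety summary counts serious events only to day 30, and no combined per-participant incidence is planned

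*Protocol*

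**What the plan says.** **Collection.** Master protocol 8.3.1 collects AEs in general until 30 days after treatment ends. For the serious and special-interest categories it goes further: "All SAEs and AESIs will be collected throughout the study period", from consent "until 90 days following last administration of study treatment". Substudy 01, 8.3.1, adds for Cohort A that "irAEs will be collected until 90 days following last administration of study treatment regardless of whether or not another anticancer therapy is initiated". The stated reason for vigilance is in Substudy 01, 6.5.4.4: irAEs may appear "several months after the last dose of pembrolizumab treatment".

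**Endpoint.** Section 3, Table 1 (and the synopsis) lists the incidence of TEAEs, of SAEs and of laboratory abnormalities. SAEs stand as their own item, with no treatment-emergent qualifier.

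**Analysis.** Section 9.4.1 defines the on-treatment period as running from first IMP "up to 30 days after the last administration of IMP". It then says: "The post-treatment period is defined as the time from the 31 days after the last administration of IMP". No end day is given for the later period. Section 9.4.3.5 puts the focus of reporting on TEAEs; its overall summary counts serious TEAEs and serious treatment-related TEAEs. For the other periods it says: "Pre-treatment and post-treatment AEs will be described separately". The same section plans SOC/PT/grade summaries of AESIs and of post-treatment AEs and SAEs, one count of Grade 5 AEs over both periods, and deaths by period.

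**The concern.** The collection window for serious, special-interest and (in Cohort A) immune-related events was set three times as long after last dose as the window for ordinary AEs, and the endpoint does not restrict SAEs to the shorter one. The figure that a reader will take as the SAE rate of the regimen is nevertheless the serious-TEAE percentage, which closes at day 30. A participant whose only SAE starts on day 45 after last dose counts as having none in that percentage.

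The post-treatment table does not repair this. The same participant may appear in both tables, so the two percentages cannot be added to give the proportion affected. At stake is a plain answer to a basic safety question for an immune combination: what fraction of participants had an SAE, or an irAE, over the period in which the trial looked for them?

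**Working it through.** **1. The plan's own safety figure.** Substudy 01, 9.2, gives the chance of seeing at least one case of an AE among 40 participants. The formula is 1 − (1 − p)^40. For p = 1%, 2% and 5% it gives 33.1%, 55.4% and 87.1%, as stated. These figures are right, but they do not say over which window the incidence p is counted.

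**2. Windows side by side, by days after last IMP.**

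| Category | Collected to | In overall TEAE summary to | Per-participant figure over both periods |
|---|---|---|---|
| AEs in general | 30 | 30 | not needed |
| Non-fatal SAEs | 90 | 30 | none planned |
| AESIs (include irAEs of Grade 3 or higher) | 90 | not listed there | separate summary, window unclear |
| irAEs of any grade, Cohort A | 90 | no irAE class listed | none planned |
| Grade 5 AEs | 90 (as SAEs) | 30 | yes, expressly pooled |

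The AESI summary is unclear for this reason. Neighbouring items in the list are labelled as TEAEs and the AESI item is not, which suggests the full window. But the whole list stands under a subheading for treatment-emergent events, which suggests day 30.

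**3. Why the separate tables cannot be added.** Let a be the number of participants with a serious TEAE and b the number with a post-treatment SAE, out of N. The number with at least one SAE lies between max(a, b) and a + b (and cannot exceed N). The planned tables do not show where in that range it lies, because the overlap is not tabulated.

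**4. Size per participant.** With N = 40, one participant whose only SAE (or irAE) starts on days 31 to 90 changes the rate by 1/40 = 2.5 percentage points.

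**5. Range under an assumption.** The documents give no late-event rate. Suppose a fraction f of the participants who have the event by day 90 have it only after day 30. If the incidence to day 90 is p, the day-30 rate is p(1 − f), and 40·p·f participants are missing from it.

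| p to day 90 | f | Day-30 rate | Missing participants of 40 |
|---|---|---|---|
| 5% | 10% | 4.5% | 0.2 |
| 5% | 40% | 3.0% | 0.8 |
| 10% | 10% | 9.0% | 0.4 |
| 10% | 40% | 6.0% | 1.6 |
| 20% | 10% | 18.0% | 0.8 |
| 20% | 40% | 12.0% | 3.2 |

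For the 5% event, the chance of at least one case in the TEAE table falls from 87.1% at f = 0 to 1 − 0.97^40 = 70.4% at f = 40%. That applies to this one table only; a late case would still show in the post-treatment table. The values of p and f are assumptions chosen to show a range.

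**The case against.** The strongest reply is that the design is coherent as written. Section 9.4.1 defines the periods, 9.4.3.5 reports each, and a 30-day TEAE window with separate post-treatment tables is no error in itself. Section 9.4 calls itself a summary and leaves detail to the SAP, which is not at hand and may add a combined table. Safety oversight does not depend on the TEAE table either: the DMC reviews cumulative data, and its ad hoc trigger in 9.5 is not limited to TEAEs.

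Most of this stands, and it rules out several stronger readings that a reader might infer:

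- *Late immune toxicity never enters a single incidence figure.* Not supported. Grade 5 AEs are pooled over both periods, and the AESI summary, which takes in irAEs of Grade 3 or higher, may already run to day 90.
- *A headline immune-related rate is understated.* No such rate is in the overall summary; irAEs as a class are not listed there for any window.
- *Most of the risk is left out for participants who stop early.* With c cycles of 21 days, days 31 to 90 make up 60/(60 + 21(c − 1) + 30) of the time from first dose to day 90: 67%, 45%, 31% and 7% for 1, 3, 6 and 35 cycles. These are shares of calendar time. They would be shares of events only under a constant hazard, for which the documents give no ground. Nor do they say that early stopping is mostly due to toxicity.

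A further fair point is that days 31 to 90 can include events after next-line therapy, since the current 8.3.1 does not stop collection when such therapy starts. That argues against making the day-90 figure the main rate; it does not argue against showing it.

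The reply does not remove the mismatch in the protocol's own text. The endpoint names SAEs without a treatment-emergent limit, collection runs to day 90, and the summary that answers the endpoint stops at day 30. One may read the endpoint's opening words as covering SAEs too, but then the endpoint should say so.

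**Conclusion.** The concern holds in a limited form. No late event goes unreported. For non-fatal SAEs, and for irAEs in Cohort A, the plan names no incidence that counts each participant once over the period in which those events are collected, and the window of the AESI summary is ambiguous. The serious-TEAE rate can equal or fall short of the day-90 SAE rate; it cannot exceed it. The gap is unknown, at 2.5 percentage points per affected participant in a cohort of 40.

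Two assumptions apply. First, the SAP does not already supply the combined figure. Second, the 90-day rule for irAEs of all grades is confirmed only for Cohort A, because the matching text of the other substudies was not available; the SAE and AESI part applies to every cohort through the master protocol. This is a worthwhile improvement in reporting, not a flaw that endangers the trial's conclusions.

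**What to change.** In 9.4.3.5:

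1. Keep the 30-day TEAE tables as they are.
2. Add beside them one incidence from first IMP to 90 days after last IMP, counting each participant once, for SAEs and AESIs in all cohorts. Do the same for irAEs in Cohort A and in any other cohort whose substudy collects irAEs to day 90.
3. State that the AESI summary covers this window.
4. Show the new figure with and without events that start after a new anticancer therapy. The schedule of activities already records the first subsequent therapy, so the split needs no new data.

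The cost is one more set of tables from data already collected. The rates may look slightly less favourable, and some events in the unrestricted figure will be attributable to next-line treatment, which is why both versions are needed.

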9.4.2 Primary endpoint(s)

9.4.2.1 Objective response rate

For all cohorts, the ORR is defined as the proportion of participants who have a confirmed CR or PR as per Investigator's assessment.

The BOR is the best overall response observed from the date of first IMP until disease progression, death, cut-off date or initiation of post-treatment anti-cancer therapy, whichever occurs first.

ORR and BOR will be summarized with descriptive statistics. In addition, two-sided 90% CIs will be computed using the Clopper-Pearson method. All objective responses need to be confirmed by a subsequent assessment performed at least 4 weeks apart from the initial response observation.

9.4.3 Secondary endpoint(s)

The secondary endpoints include safety, efficacy (TTR, DoR, CBR, PFS per RECIST 1.1), immunogenicity, and PK.

9.4.3.1 Time to response

Time to response will be assessed on the subgroup of participants who have achieved confirmed objective response in the efficacy population.

Time to response will be defined as the time from the date of first IMP administration to the first tumor assessment at which the overall response was recorded as PR or CR that is subsequently confirmed.

9.4.3.2 Duration of response

The DoR will only be summarized on the subgroup of participants who have achieved confirmed objective response in the efficacy population.

The duration of response will be defined as the time from the date of first tumor assessment at which the overall response was recorded as CR or PR that is subsequently confirmed to the date of first documentation of objective progressive disease before the initiation of any post-treatment anti-cancer therapy or death due to any cause, whichever occurs first. In the absence of disease progression or death before cut-off date, DOR will be censored at the date of the last valid tumor assessment performed before the cut-off date or date of initiation of new anti-cancer therapy, whichever is earlier.

Duration of response will be summarized with descriptive statistics using Kaplan-Meier methods. The median DoR and associated 90% CI will be provided.

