- o CT/MRI: The initial tumor imaging will be performed within 28 days prior to C1D1. Scans performed as part of routine clinical management are acceptable for use as the screening scan if they are of diagnostic quality and performed within 28 days prior to the date of enrollment. On study imaging will be performed every 9 weeks (63 ± 7 days) after the date of first IMP and if clinically indicated. Imaging studies should follow calendar days and should not be adjusted for delays in cycle starts or extension. The same imaging technique should be used in a participant throughout the trial. After week 45, tumor imaging should be performed every 12 weeks (84 ± 7 days). CT scan of the chest, abdomen, pelvis and any other locations with suspicion or evidence of disease involvement is required for the baseline assessment, during treatment period until PD. Per the primary tumor assessment criteria, after the first documentation of response or the first documentation of progression (if the participant is clinically stable), confirmatory imaging may be performed no fewer than 28 days later. Alternately, the scan performed at the next scheduled time point (eg, every 63 ± 7 days) may be used as confirmation. Tumor assessment is not needed for participants who start another anti-cancer therapy.

Abbreviations: ADA=anti-drug antibodies; AE=adverse event; AST=aspartate transaminase; ALT=alanine transaminase; C=Cycle; ANC=Absolute neutrophil count; AP=Alkaline phosphatase; BUN=Blood urea nitrogen; CRF=case report form; CRS=Cytokine release syndrome; CT=computed tomography; [REDACTED]; D=Day; ECG=electrocardiogram; ECOG=Eastern Cooperative Oncology Group; e-CRF=electronic case report form; EOT=end-of-treatment; FT4=free thyroxine; FU=follow-up; HBsAg=Hepatitis B surface antigen; HCV=Hepatitis C virus; ICF=Informed consent form; IMP=investigational med [REDACTED] ed ratio; LDH=Lactate hydrogenase; LVEF=left ventricular ejection fraction; MRI=magnetic resonance imaging; MUGA= multigated acquisition; PD=progressive disease [REDACTED] PDy=pharmacodynamic; PK=pharmacokinetic; PR=partial response; PS=Performance Status; SpO2= oxygen saturation; Q3W=every 3 weeks; RECIST=Response Evaluation Criteria in Solid Tumors; SAE=serious adverse event; T3=tri-iodothyronine; TSH=thyroid stimulating hormone; WBC=White blood cells.

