3 OBJECTIVES AND ENDPOINTS

Table 1 - Objectives and endpoints

Objectives	Endpoints
Primary	
• To determine the antitumor activity of SAR444245 in combination with other anticancer therapies• Objective response rate (ORR) defined as the proportion of participants who have a confirmed complete response (CR) or partial response (PR) determined by Investigator per Response Evaluation Criteria in Solid Tumors (RECIST) 1.1 (1)
Secondary	
• To assess the safety of SAR444245 in combination with other anticancer therapies• To assess other indicators of antitumor activity• Incidence of treatment emergent adverse events (TEAEs), serious adverse events (SAEs), laboratory abnormalities according to National Cancer Institute Common Terminology Criteria for Adverse Events (NCI CTCAE) V5.0 and American Society for Transplantation and Cellular Therapy (ASTCT) consensus grading (2)• Time to response (TTR), defined as the time from the first administration of investigational medicinal product (IMP) to the first tumor assessment at which the overall response was recorded as PR or CR that is subsequently confirmed and determined by Investigator per RECIST 1.1• Duration of response (DoR), defined as the time from first tumor assessment at which the overall response was recorded as CR or PR that is subsequently confirmed until documented progressive disease (PD) determined by Investigator per RECIST 1.1 or death from any cause, whichever occurs first• Clinical benefit rate (CBR) including confirmed CR or PR at any time or stable disease (SD) of at least 6 months determined by Investigator per RECIST 1.1.• Progression-free survival (PFS), defined as the time from the date of first IMP administration to the date of the first documented disease progression determined by Investigator as per RECIST 1.1 or death due to any cause, whichever occurs first• Plasma concentrations and where applicable PK parameters of SAR444245• Incidence of anti-drug antibodies (ADAs) against SAR444245
Exploratory	

For China, please see [Section 10.7](#) for details.

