 2. Participants who discontinue study treatment **with PD** will be followed for safety in the Follow-Up Visit 1 occurring 3 months \pm 7 days from last IMP administration, before moving to the Survival Phone Call Follow-Up Period.

Participants who move into the **Survival Phone Call Follow-Up Period** will be contacted by telephone every 3 months \pm 14 days to assess for survival status. Updated survival status may be requested by the Sponsor at any time during the study. Survival Phone Call Follow-up will continue until death, participant request to discontinue from follow-up, or cut-off date for the given cohort final analysis has been reached, or upon cancellation of Survival follow-up in the given cohort at the discretion of the Sponsor at any prior timepoint whichever occurs first.

The cohort cut-off for the primary ORR endpoint analysis for each individual cohort is estimated to be approximately 9 months from the date of the last participant first infusion. This would allow the possibility to observe the response of the last participant for 6 months, assuming there is a response at first treatment assessment.

After the cohort cut-off date for the primary ORR analysis, participants can continue to receive IMP, if clinical benefit is observed, until full permanent discontinuation criteria described in **Section 7** are met and will continue to undergo all assessments as per the study schedule of activities.

For each cohort, the cut-off date for the final analysis (ie, analysis of secondary objectives and update of primary objective) will be 18 months from the corresponding cohort LPI. After this cut-off date for the final analysis, the participants of the given cohort still receiving study treatment in that specific cohort will be followed up as the cohorts after early termination described in **Section 10.1.9**.

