9.4.3.4 Progression-free survival (RECIST 1.1)

Progression-free survival is defined as the time from the date of first IMP to the date of the first documentation of objective progressive disease or death due to any cause, whichever occurs first.

The analysis of PFS will be based on the following censoring rules:

- If progression or death is not observed before the cut-off date and prior to the initiation of a further anticancer therapy, then PFS will be censored at the date of the last valid tumor assessment performed before the cut-off date or date of initiation of a further anticancer therapy, whichever is earlier.
- A participant without event (death or disease progression) and without any valid post-baseline tumor assessment will be censored at the day of first IMP (Day 1).

Progression-free survival will be summarized using Kaplan-Meier methods. The median PFS times and associated 90% CI will be provided.

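### A responder's death after new anticancer therapy counts as a DoR event but is censored for PFS, so DoR can end after PFS and its censoring depends on later survival

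*Protocol*

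**What the plan says.** Section 9.4.3.2 of the master protocol starts DoR at the first assessment showing a response, provided a later scan confirms it. The end of the interval is worded as follows: "to the date of first documentation of objective progressive disease before the initiation of any post-treatment anti-cancer therapy or death due to any cause". A separate sentence gives the censoring rule: "In the absence of disease progression or death before cut-off date, DOR will be censored at the date of the last valid tumor assessment". That scan must precede both the cut-off and any new anticancer therapy.

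Section 9.4.3.4 states the PFS condition differently: "If progression or death is not observed before the cut-off date and prior to the initiation of a further anticancer therapy". When this condition is met, PFS is censored at the latest valid scan that precedes both the cut-off and any further therapy.

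The endpoint definition in section 3 (repeated in the synopsis) does not mention new therapy; DoR there simply runs "until documented progressive disease (PD) determined by Investigator per RECIST 1.1 or death from any cause, whichever occurs first".

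Two operational rules matter here. Scanning stops once another therapy starts (section 1.3, imaging footnote): "Tumor assessment is not needed for participants who start another anti-cancer therapy". Survival follow-up continues: people in that phase "will be contacted by telephone every 3 months" (section 4.1), with the cohort's final cut-off as one of the stopping points.

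**The concern.** In the DoR definition the new-therapy limit qualifies progression, while death carries no limit. The censoring sentence is conditional on there being no death before cut-off, so it is never reached for a participant who dies after new therapy and before cut-off. For PFS, the new-therapy condition covers both kinds of event.

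Two things follow. First, the same death is an event for one endpoint and censored for the other, and a responder's DoR can end later than that responder's PFS. Second, among responders who start new therapy without progression, those alive at cut-off are censored back at their last scan, while those who have died are carried forward to death. Censoring then depends on what happens afterwards, which conflicts with the independent censoring that the Kaplan-Meier method (named in 9.4.3.2) assumes. DoR for those who die also includes time on the next regimen.

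The case can arise. Participants may stop treatment without progression and start another therapy (section 4.1). Scans then end, so death is in practice the DoR event that can still be seen.

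**Working it through.** The protocol states no DoR or PFS figure to reproduce. The check applies the two rules, as written, to one responder and then to a small set.

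**Inputs from the protocol.** Scans every 63 days (section 8.1.1); the event and censoring rules of 9.4.3.2 and 9.4.3.4.

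**Assumed dates.** First dose day 0; response day 63; confirming and last scan day 126; new therapy day 140 without progression; cut-off day 540.

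**Rules applied.**
- DoR as written: if death falls on or before day 540, DoR = death day − 63, event. Otherwise DoR = 126 − 63 = 63 days, censored.
- PFS as written: any death after day 140 fails the new-therapy condition, so PFS = 126 days, censored.

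| Death on day | DoR as written | PFS as written |
|---|---|---|
| 160 | 160 − 63 = 97, event | 126, censored |
| 200 | 200 − 63 = 137, event | 126, censored |
| 300 | 300 − 63 = 237, event | 126, censored |
| 400 | 400 − 63 = 337, event | 126, censored |
| 500 | 500 − 63 = 437, event | 126, censored |
| none by day 540 | 126 − 63 = 63, censored | 126, censored |

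In every row with a death, DoR ends on a later calendar day than PFS. Once death is later than day 126 + 63 = 189, DoR is also longer in days, although it starts 63 days later. The last row shows the dependence on survival: alive at cut-off, the same responder contributes 63 censored days.

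**Effect on a median (assumed set of eight).** Six unaffected responders have DoR 126, 126, 189, 252 and 315 days (events) and 378 days (censored). The other two started new therapy without progression and later died. The median is taken as the first time the curve is at or below 0.5.
- As written, with the two at 300 and 337 days (events): the curve is 7/8, 6/8, 5/8, then 4/8 = 0.5 at day 252. Median 252 days.
- Under the PFS rule, both are censored at day 63, leaving six at risk: 5/6, 4/6, then 3/6 = 0.5 at day 189. Median 189 days.
- As written, but with both deaths on day 160 (DoR 97 days each): 6/8 after day 97, then 4/8 = 0.5 at day 126. Median 126 days.

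**One affected case among seven.** Keep the same six and add one responder at 337 days (event): 6/7, 5/7, 4/7 at day 189, then 3/7 at day 252, so the median is 252 days. Censored at day 63 instead, the curve is again 3/6 at day 189, so the median is 189 days.

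The shift can go in either direction, depending on how soon death follows the new therapy.

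**Weight of one case.** Table 9 of substudy 01 lists 2 to 14 responders out of 40. With 8 responders one case is 1/8 = 12.5% of the DoR sample; with 4 it is 1/4 = 25%.

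**The case against.** The strongest reply is that this is loose drafting. Both sections use nearly the same censoring date, which suggests a common intent, and the new-therapy phrase in 9.4.3.2 may simply be misplaced. The PFS clause is loosely built too. That may be so, but the DoR sentence as it stands does not produce the PFS rule, and the same edit cures it.

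A second reply is that counting every death matches the definition in section 3 and is a legitimate convention. That stands as far as the convention goes, and is why a version counting all deaths can be kept as a sensitivity analysis. The rule as written does not apply it consistently, however: it ignores new therapy for those who die and censors for it in those who survive.

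A third is that the statistical analysis plan, not available for this review, may settle the matter. It may, but the two protocol rules already differ.

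The reply on size largely stands. The affected participant must have a confirmed response, start new therapy without documented progression, and die before cut-off. Treatment normally continues to progression, and other systemic anticancer therapy is prohibited during treatment (section 6.8.2). All dates above are assumed, and nothing in the protocol says how often this would happen.

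Two stronger inferences are not supported:
- A reader might infer that progression documented after new therapy falls outside both the event and the censoring rule. The censoring sentence directly follows the definition of qualifying progression, so later progression is naturally read as non-qualifying and the participant as censored; scans are not required then anyway.
- A reader might infer that the DoR and PFS tables would contradict each other. They would handle one kind of death differently, which is an inconsistency of rule, not a contradiction of results.

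**Conclusion.** The point holds for deaths after new anticancer therapy. Read as written, 9.4.3.2 and 9.4.3.4 treat the same death differently, DoR can end after PFS for the same responder, and DoR censoring depends on later survival. No text in the protocol reconciles the two.

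The size is limited. DoR is a secondary endpoint, the study tests no hypothesis (section 9.1), and the 90% intervals are descriptive (section 9.4.1). The futility rule in substudy 01 section 9.5 uses ORR, so it is unaffected. The protocol rests no formal durability claim on the median DoR. Few participants are likely to be affected and the shift in a real cohort could be nil. With a handful of responders, one or two cases could still move the median, as the assumed sets show. The conclusion about the rules rests on their wording alone; the size rests on the assumed dates and responder sets.

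**What to change.** Align 9.4.3.2 with 9.4.3.4. Define a DoR event as the first documented progression or death, either one occurring before any new anticancer therapy and before the cut-off. In all other cases, censor DoR at the last valid tumor assessment before the earlier of the cut-off and the start of new therapy. Carry the same wording into the statistical analysis plan. The version that counts all deaths can be shown as a sensitivity analysis.

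With this rule the example responder has DoR of 63 days and PFS of 126 days, both censored on day 126 whatever the later survival, and a responder's DoR cannot end after PFS. The cost is one sentence, plus a few DoR events that become censored, which gives slightly less information on an already small sample.
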